10.1 Participant Identification

Potentially eligible participants will be identified by screening medical records or through clinic consultations, and then given or sent an invitation letter and participant information sheets by the local PI/research team. This will ask if they would like to learn more about the trial or if they do not want to be contacted about it again. Further trial information participant materials including signposting to the trial website where a range of resources regarding the trial will be posted and a video(s) about the trial will be available too. Alternative means of participant identification maybe through participant's self-interest in the trial via its website. This will entail potential participants contacting their most local participating site via details on the trial website.

10.2 Consent

The Informed Consent Form (ICF) must be approved by the Research Ethics Committee (REC) and must be in compliance with GCP, local regulatory requirements and legal requirements. The investigator or designee must ensure that each trial participant, is fully informed about the nature and objectives of the trial and possible risks associated with their participation.

The investigator or their designee will obtain written informed consent from each participant before any trial-specific activity is performed. The ICF used for this trial and any change made during the course of this trial will be approved by the REC. One copy of the ICF will be kept by the participant, one will be retained by the research site; original to be kept in medical notes.

If consent is conducted in person, both the investigator or their designee and the participant shall sign and date the ICF. In the event that consent is obtained remotely, the participant only shall sign and date the consent form, and the investigator or designee will sign and date the corresponding Confirmation of Consent Process form. Both these forms will be required for full evidence of consent. Further details of the remote consent procedure can be found in the TPM.

The consent will include permission for:

- electronic record linkage via NHS Digital to the Office of National Statistics (ONS) for mortality and hospital episodes statistics (HES)
- access by the research team to hospital records where necessary for the purposes of trial outcome measures.
- central coordinating trial team and/or central pharmacy will have access to participant details to enable conduct of the trial if required (i.e. for coordination of home delivery of medication).

For the purpose of oversight and audit inspection of the trial, the lead site central coordinating team will be sent a copy of the ICF (and additionally Confirmation of Consent Process form where remote consent process is used). These forms will be sent to check they are being completed correctly. The lead site central coordinating team will destroy the copy of ICF (and Confirmation of Consent Process) as per NHS confidential waste standard, once the checks have been made. Forms will be sent using secure transfer methods (e.g. nhs.net to nhs.net email)

Should a participant require a verbal translation of the trial documentation during the consent process by a locally approved interpreter/translator, it is the responsibility of the individual investigator to use locally approved translators.

If the trial requires participant-facing documentation in a different language (other than English), the translation and back translation documents need to be reviewed and approved by the Sponsor prior to use. All sections of the approved documents must appear in the translation. The translated version must be appropriately dated and include version control.

Any new information which becomes available, which might affect the participant's willingness to continue participating in the trial will be communicated to the participant as soon as possible. This new information will be provided either verbally over the telephone or in writing by post.

Additional consent for ancillary studies

Participants will be asked if they consent to receive invitations and information for any further associated ancillary/substudies studies that may arise from the OPACE pilot phase.

10.3 Screening Evaluation

Inclusion and exclusion criteria as per sections 8.1 and 8.2 will be used in screening evaluation.

Screening and baseline visit (i.e. trial visit 1) can be performed at the same visit if required. Information regarding reasons why patients were not eligible for the trial will be collated. If the patient was eligible but declined to take part, this will also be recorded on screening logs.

A participant can be re-screened for eligibility for participating in the trial during the active recruitment phase of the trial project, if they are experiencing a COPD exacerbation at the time of screening, but subsequently become stable in their COPD, for example.

10.3.1 Screening Assessments

There are no specific screening assessments as part of the trial and eligibility is determined by inclusion and exclusion criteria. Assessment of eligibility will be undertaken at screening and re-evaluated as needed prior and within baseline visit and consent consultation. There is no specific time period from screening to baseline visit. ECGs will not be used during screening of potential participants, since participants are already prescribed and on azithromycin via a clinical care pathway. ECGs may be undertaken as part of routine clinical care at any time during the trial if clinically indicated. Trial specific assessments will only be conducted after participants have given written informed consent.

Current breast feeding, pregnancy or planned pregnancy during the trial is an exclusion criterion of the trial. Pregnancy testing will not be conducted at screening.

10.3.2 Participant Registration/Randomisation

Following informed consent, each participant will be registered and provided with a unique trial ID. Participant registration is needed before any other visits and data collection can be scheduled. Randomisation will then take place via Sealed Envelope (SE). Further information on data collection variables and trial assessments are provided in the TPM.

10.4 Trial Assessments

This is a pragmatic trial and as such the assessments included are to answer the trial objectives only and preserve ecology of standard of care practice as much as possible. Medical history, smoking history and drug/medication history will be recorded in the trial based on participant reported information and may be corroborated with healthcare records. This will include COVID and influenza vaccination status and medications that participants are prescribed including for their COPD.

Exacerbations are a key part of the outcome measures of the trial. The exacerbation history of a patient at baseline is also important. Further detail regarding aspects of exacerbations are provided below:

10.4.1 Exacerbation definition

The ATS/ERS guideline definition of a COPD exacerbation will be used: i.e. a worsening of patient's COPD symptoms beyond day-to-day variability sufficient to warrant a change in management. The minimum change in management for definition of an exacerbation for the trial is requiring treatment with additional antibiotics and/or oral corticosteroids.⁴⁵ A minimum of two weeks between exacerbations is necessary to consider them as separate exacerbations.⁴⁶ Exacerbation severity will be ascertained (i.e. moderate is use of additional antibiotics and oral steroids, severe is requirement of hospitalisation).^{1, 45, 46}

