7.8 Trial Outcome Measures

7.8.1 Primary outcome measure

Time to first COPD exacerbation.

7.8.2 Secondary outcome measures

Data pertaining to secondary outcomes will be collected over the entire trial follow-up (i.e. inclusive of time on IMP and if needed off IMP):

- Number/rate of exacerbations (and differentiation by severity of exacerbations, i.e. requirement of hospitalisation)
- Length of exacerbation-free status
- Antibiotics and/or corticosteroids use for respiratory indication
- Symptoms/impact: CAT score and cough visual analogue score (VAS)
- Health status (quality of life measured by change in EQ-5D-5L)
- Mortality (all cause and specific)
- Healthcare utilisation (for health economic analysis)
- Adverse events of special interest (AESI) (including cardiovascular and hearingdefined as new prescription of hearing aids, liver function test (LFT) dysfunction), serious adverse events (SAEs)
- Sputum culture results, if clinically indicated and sample via routine clinical care to local lab. Record if positive result (i.e. name of organism cultured only, not cfu/ml). If multiple sent, most recent one to trial visit should be used.
- Adherence to trial medication.

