13 EVALUATION OF RESULTS (DEFINITIONS AND RESPONSE/EVALUATION OF OUTCOME MEASURES)

13.1 Response criteria

13.1.1 Exacerbations Primary endpoint is time to first exacerbation.

Secondary endpoint is number/rate and severity of exacerbations (i.e. moderate and/or severe). These will be patient reported and recorded in the database.

13.1.2 Survival

This will be measured from the date of randomisation and will be reported for all deaths. The cause of death is to be recorded in all instances where possible. All-cause mortality, respiratory/COPD-related and cardiovascular mortality will be collated.

13.1.3 Quality of life, anxiety and depression

EQ-5D-5L will be used to assess quality of life. GAD-2 and PHQ-2 will assess levels of anxiety and depression.

13.1.4 Symptoms

These will be assessed by the CAT score and cough VAS.

The self-rated health status (SHS) will assess level of frailty in participants.

Healthcare usage for their COPD will be assessed throughout their trial follow-ups.

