15 STATISTICS

15.1 Statistical Methods

A Statistical Analysis Plan (SAP) will be written and approved by the TSC and NIHR. A version of the SAP outlining the key aspects of the primary analysis, will be produced before any efficacy data is examined by the independent data monitoring committee (iDMC), TSC, or any members of the trial team. An interim SAP will be produced before any interim analysis is performed.

The primary endpoint is time to first exacerbation. The experimental treatments are complete discontinuation, seasonal discontinuation, and the control arm is continued azithromycin (this is standard of care). The hazard ratio comparing the two experimental arms to control will be estimated using a Cox proportional hazards model, adjusting for pre-randomisation factors of exacerbations history (number in preceding 12 months) and recruitment site. The consensus decision of the project team was that recruitment site and history of previous exacerbations (given this is the strongest predictor of exacerbations) are appropriate pre-specified covariates. Formal inference will compare the 1-sided confidence interval to the non-inferiority margin of a hazard ratio of 1.25. If the interval lies entirely below 1.25 then a conclusion of non-inferiority will be made. The confidence intervals will be at a 97.3% level, to adjust for there being two comparisons, and thus preserve an overall 5% significance level. The primary analysis will be an Intention to Treat analysis.

For the panel of subgroup factors to consider (section 15.1.1-15.1.2), the analysis will estimate the main effect and a treatment-subgroup interaction on the hazard ratio scale, adjusting for baseline covariates used in the primary analysis. This will be carried out in a univariate fashion, looking at each subgroup individually. Potentially, a multivariate model will be developed to include multiple subgroups simultaneously and provide a risk score. Standard 95% confidence intervals for the estimated subgroup-treatment interaction hazard ratio will be the primary focus. Multiple testing would preclude making strong claims of formal statistical significance; and any personalised treatment strategy would need to be validated in future research.

Secondary endpoints will be analysed using a similar regression methodology, as suitable for the nature of the endpoint (binary, categorical, continuous, time-to-event). The rate of

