exacerbations will be evaluated by dividing number of exacerbations by person-years of follow-up and will be analysed with both Poisson and negative-binomial analyses.

Missing data will be quantified for each endpoint broken down by treatment arm. The reference analyses will assume missing at random, conditional on the baseline covariates used for adjustment. Should the rate of missing data exceed 10%, then multiple imputation will be used in sensitivity analyses that consider alternative assumptions incorporating selection bias.

15.1.1 Pre-specified subgroup analysis

The aim of this subgroup analysis is to identify factors that may practically support front line clinicians in shared decision making for individual patients. Selection of subgroup variables have been considered in-depth based on post-hoc evidence of azithromycin prophylaxis trials in COPD, and consideration of generalisability to clinical practice. The limitations of subgroup analyses are recognised. We have tried to limit multiplicity and plan to undertake and report subgroup analysis as per recommended criteria.⁶³ Subgroup analysis will be performed for the trial's primary endpoint, as well as secondary outcomes of exacerbation rate (including severe exacerbations analysed separately) and side effects/risks, evaluated on IMP.

15.1.2 Top priority subgroup analysis:

- Exacerbation history (number in last 12 months): Strongest predictor of future exacerbations.³⁵
- **FEV1 %:** In two trials milder airflow obstruction was associated with greater treatment efficacy of azithromycin in COPD, although trial populations may not be reflective of real-world COPD patients prescribed azithromycin. (i.e. one trial-not frequent exacerbators, other included GOLD stage 1).^{4,31,43}
- **Smoking status:** Current smoking may affect azithromycin efficacy.³¹ Important to evaluate, NICE recommend only in non-smokers specifically, BTS recommend smoking cessation optimisation prior to starting treatment.^{1,2}
- **CAT score (symptom burden/impact):** NICE recommend evaluation of prognostic factors in COPD care because of potential therapy implications.¹ Of prognostic factors, CAT score is likely most useful to evaluate.

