15.3 Participant Numbers

This is an event-driven, non-inferiority trial, where the sample size and duration of follow-up is dependent on the number of primary endpoint (time to first exacerbation) events that occur. Estimation of the number of events required and therefore modelling of sample size required to achieve this number of events is based on available evidence.

Assuming a median time to first exacerbation (TTFE) of 150 days^{4,9,43} in the control standard of care arm (continuous treatment), and a non-inferiority threshold of 30 days, equates to the threshold on the hazard ratio scale of 1.25. The non-inferiority threshold of 30 days selected, was judged by respiratory specialists to be a clinically relevant margin of TTFE. There are no validated minimum clinically important differences for COPD exacerbations, including time free or until a COPD exacerbation. Given that a 2-week window between exacerbations is often used to define separate events,⁴⁶ TTFEs reviewed in azithromycin trials,^{4,9,43} as well as TTFE in a large non-inferiority COPD treatment trial (FLAME trial),⁶⁴ all support 30 days as a reasonable non-inferiority margin.

Sample size is based on 90% power for two non-inferiority comparisons (seasonal and placebo compared with continuous as standard treatment), at 2.7% significance (Dunnett test for multiple comparisons) using a Cox proportional hazards model. The number of primary endpoints required is **1242**. We assume a recruitment rate of ~560-630 participants per year,^{48,50} and a recruitment period of 29 months.

The total **sample size** estimate is thus **1311 (n=437 per arm)** and allows for $\sim 5\%$ dropout before the primary endpoint (first exacerbation), or censoring, to achieve the required 1242 events.

Data from previous withdrawal trials of corticosteroids^{65,66} suggest that adverse events (COPD exacerbations predominantly) was the main reason for dropouts. Given that our primary endpoint is TTFE, and that the expected median time to the primary event is approximately 5 months, only a tiny number of dropouts should happen before the primary event occurs. The anticipated median follow-up period of 24 months for the trial cohort is

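### Section 10.4.1 counts exacerbations treated with one drug as events but defines moderate as needing both drugs, so single-drug exacerbations managed without hospitalisation have no severity class

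*Protocol*

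**What the plan says.** Section 10.4.1 sets the minimum change in management for a trial exacerbation as "requiring treatment with additional antibiotics and/or oral corticosteroids". Either drug alone is enough. The same paragraph then defines severity: "moderate is use of additional antibiotics and oral steroids, severe is requirement of hospitalisation". The protocol defines no mild or other class.

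Severity appears in four other places:

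- Section 7.7.2 makes the number or rate of exacerbations and their severity part of the first secondary objective.
- Section 7.8.2 lists the number or rate as a secondary outcome, with "differentiation by severity of exacerbations, i.e. requirement of hospitalisation".
- Section 13.1.1 states: "Secondary endpoint is number/rate and severity of exacerbations (i.e. moderate and/or severe".
- Section 15.1.1 plans subgroup analyses of "exacerbation rate (including severe exacerbations analysed separately").

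The primary outcome in section 7.8.1 is "Time to first COPD exacerbation", with no severity condition. Section 15.1 obtains the rate by dividing the number of exacerbations by person-years, again with no severity condition.

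**The concern.** The event definition joins the two drugs with *and/or*; the moderate definition joins them with *and*. Under the text as written, an exacerbation treated outside hospital with an antibiotic alone, or a steroid alone, is a counted event. It fails the moderate definition because only one drug was given, and the severe definition because there was no admission.

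What is at stake is the severity part of a named secondary endpoint. Two analysts could report different moderate counts from the same data and each cite the protocol. One would count only events treated with both drugs (section 10.4.1). The other would count every event without hospitalisation (the split in section 7.8.2). Events are reported as they occur across about 135 planned sites, so if sites assign the class, coding could also differ between them.

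**Working it through.** **1. Classification under the text as written.** The inputs are the event rule and the two severity rules in section 10.4.1. A qualifying event with hospitalisation is placed in the severe class. All combinations of antibiotic, oral steroid and hospitalisation were listed:

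| Antibiotic | Oral steroid | Hospitalised | Trial event? | Class as written | Class with *and/or*, not hospitalised |
|---|---|---|---|---|---|
| yes | no | no | yes | **none** | moderate |
| no | yes | no | yes | **none** | moderate |
| yes | yes | no | yes | moderate | moderate |
| yes | no | yes | yes | severe | severe |
| no | yes | yes | yes | severe | severe |
| yes | yes | yes | yes | severe | severe |

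The two combinations with neither drug do not meet the minimum treatment rule and are not trial events. Of the six that are, 4 have a class as written and 6 − 4 = 2 do not. With *and/or* in the moderate definition, all 6 have exactly one class.

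**2. Consistency between sections.** As written:

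- all exacerbations = moderate + severe + unclassified (single drug, not hospitalised).

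Section 7.8.2 divides events by hospitalisation, which implies:

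- all exacerbations = hospitalised + not hospitalised.

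The severe and hospitalised categories agree. The moderate and not-hospitalised categories differ by exactly the unclassified events. Section 13.1.1 names only moderate and severe, so it offers no place for them.

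**3. Whether the sample size is touched.** Section 15.3 gives 90% power "at 2.7% significance (Dunnett test for multiple comparisons) using a Cox proportional hazards model", and section 15.1 states "Formal inference will compare the 1-sided confidence interval to the non-inferiority margin of a hazard ratio of 1.25". By Schoenfeld's formula for one comparison with equal allocation:

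- events = 4 × (z₀.₉₇₃ + z₀.₉₀)² / (ln 1.25)² = 4 × (1.927 + 1.282)² / (0.2231)² ≈ 827;
- three arms: 827 × 3/2 = 1240.5, against 1242 (3 × 414) stated;
- 5% dropout: 1242 / 0.95 = 1307.4, so 1308, against 1311 stated.

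The protocol's figures reproduce closely. They rest on first exacerbations of any severity, so the moderate definition does not enter them.

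**4. Size of the undercount.** It equals the number of single-drug exacerbations managed without hospitalisation. The protocol gives neither the share treated with one drug nor the share hospitalised, so no figure can be derived.

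**The case against.** The best reply is that the *and* looks like a drafting slip and that little depends on it. Section 7.8.2, the outcome list, separates events by hospitalisation and leaves none out. Section 15.1 computes the rate from all exacerbations. The only severity-specific analysis the protocol names is of severe events, and that definition is sound. No separate model for moderate events is specified. All of this stands, and it limits the point to the moderate category.

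It does not remove the point. Section 7.8.2 shows what was probably meant, but it does not rewrite the explicit moderate definition in section 10.4.1, and section 13.1.1 uses that term for an endpoint. A slip in an outcome definition still has to be corrected.

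A reader might go further in three ways that the protocol does not support:

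- *That the primary and secondary endpoints count different events.* This treats the bracket in section 13.1.1 as limiting which events enter the number or rate. The bracket more naturally explains the word severity, and sections 7.8.2 and 15.1 put no severity filter on the count.
- *That the loss of events or precision can be estimated.* This would need an assumed single-drug share, the removal of hospitalised events (which are always classed), and a recurrent rate extrapolated from a median time to a first event. None of these gives a firm basis.
- *That the moderate class would reflect prescribing only because of this wording.* The event definition is itself based on treatment, and so is the corrected wording. The literal rule adds only a further dependence on whether one drug or two were given.

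**Conclusion.** The moderate definition in section 10.4.1 is wrong as written. It leaves two of the six qualifying combinations, the single-drug events without hospitalisation, outside every severity class. The moderate category in section 13.1.1 would be undercounted and would disagree with the split in section 7.8.2.

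The effect stops there. Time to first exacerbation, the total rate, the analysis of severe events, the 1242 events and the 1311 participants do not change. The amount of undercounting is unknown.

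The conclusion rests on reading *and* literally and on the absence of any other severity class in the protocol. Only the protocol was available. A statistical analysis plan could add a working rule, but the protocol text would still need to agree with it.

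**What to change.** Bring sections 10.4.1, 7.8.2 and 13.1.1 into line:

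- Moderate: an exacerbation treated with additional antibiotics and/or oral corticosteroids, without hospitalisation.
- Severe: an exacerbation requiring hospitalisation.
- Section 13.1.1: state that the number and rate count every exacerbation meeting the definition in section 10.4.1, and that moderate and severe are the two parts of that total.

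This changes an outcome label only. It alters no treatment, no primary analysis and no sample size. The cost is a short wording amendment through the route in section 18.4, plus matching text in any site guidance that assigns severity.

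The case report form is not part of the protocol, so the trial team should check that it records hospitalisation and each drug class for every event. Section 7.8.2 already lists antibiotic and corticosteroid use for respiratory indications as an outcome, and section 10.4.3 provides a diary for the details of each exacerbation. If both are captured per event, exacerbations already recorded can be reclassified centrally.
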